## 4.2. Scientific rationale for study design

RSV is associated with serious illness in OA and high-risk adults, including those with chronic lung and heart disease or other co-morbidities that may lead to increased risk of RSV-LRTD. The efficacy of a single dose of the RSVPreF3 OA investigational vaccine in the prevention of RSV-LRTD in OA ≥60 YOA has been shown in the Phase 3 clinical study RSV OA=ADJ-006 (refer to IB). The current study is designed as a Phase 3, observer-blind, placebo-controlled study to demonstrate the NI of the immune response and evaluate safety of RSVPreF3 OA investigational vaccine in adults 50-59 YOA, including those who are at increased risk of RSV-LRTD, compared to adults ≥60 YOA.

The inclusion of a group of healthy adults (50-59 YOA) will document the immunogenicity in adults and in the population of OA, since immunogenicity might be impacted by disease and/or age in both those groups.

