# 6.3.2. Randomization to study intervention

- Participants in Cohort 1, Adults-HA Sub-cohort will be randomly assigned to the Adults-HA-RSV Group and Adults-HA-Placebo Group in a 2:1 ratio at Visit 1 (Day 1) to receive the RSVPreF3 OA investigational vaccine or placebo, respectively.
- Participants in Cohort 1, Adults-AIR Sub-cohort will be randomly assigned to the Adults-AIR-RSV Group and Adults-AIR-Placebo Group in a 2:1 ratio at Visit 1 (Day 1) to receive the RSVPreF3 OA investigational vaccine or placebo, respectively.
- All participants in Cohort 2 (OA-RSV Group) will be assigned to receive the RSVPreF3 OA investigational vaccine.

The randomization of supplies within blocks will be performed at GSK, using MAtEx, a program developed for use in SAS (Cary, NC, US) by GSK. Entire blocks will be shipped to the study centers/warehouse(s).

To allow GSK to take advantage of greater rates of recruitment in this multi-center study and to thus reduce the overall study recruitment period, an over-randomization of supplies will be prepared.

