# 9. STATISTICAL CONSIDERATIONS

# 9.1. Statistical hypotheses

Statistical hypotheses are associated to the confirmatory primary NI objectives, which will be tested according to the graphical procedure detailed in Section 9.3.1. Global type I error is controlled at 2.5% (1-sided).

Table 14 Study objectives and null hypothesis

	Objectives		Null hypothesis	
	Prin	mary		
•	To demonstrate the NI of the humoral immune response in healthy participants 50-59 YOA compared to OA (≥60 YOA) for the RSV-A strain after RSVPreF3 OA investigational vaccine administration.	•	Null hypothesis 1 (H1): The anti-RSV-A GMT ratio (OA-RSV Group over Adults-HA-RSV Group) is >1.5 or the SRR difference (OA-RSV Group – Adults-HA-RSV Group) is >10% at 1 month post RSVPreF3 OA vaccine administration. This must be rejected in favor of the alternative hypothesis that the GMT ratio is ≤1.5 and the SRR difference is ≤10%.	
•	To demonstrate the NI of the humoral immune response in healthy participants 50-59 YOA compared to OA (≥60 YOA) for the RSV-B strain after RSVPreF3 OA investigational vaccine administration.	•	Null hypothesis 2 (H2): The anti-RSV-B GMT ratio (OA-RSV Group over Adults-HA-RSV Group) is >1.5 or the SRR difference (OA-RSV Group – Adults-HA-RSV Group) is >10% at 1 month post RSVPreF3 OA vaccine administration. This must be rejected in favor of the alternative hypothesis that the GMT ratio is ≤1.5 and the SRR difference is ≤10%.	
•	To demonstrate the NI of the humoral immune response in participants 50-59 YOA at increased risk of RSV-LRTD compared to OA (≥60 YOA) for the RSV-A strain after RSVPreF3 OA investigational vaccine administration.	•	Null hypothesis 3 (H3): The anti-RSV-A GMT ratio (OA-RSV Group over Adults-AIR-RSV Group) is >1.5 or the SRR difference (OA-RSV Group – Adults-AIR-RSV Group) is >10% at 1 month post RSVPreF3 OA vaccine administration. This must be rejected in favor of the alternative hypothesis that the GMT ratio is ≤1.5 and the SRR difference is ≤10%.	

219238 (RSV OA=ADJ-018) Protocol Final

	Objectives		Null hypothesis

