# 9.3.1. Primary endpoints/estimands analysis

[figure not shown]
Considering the sampling timepoint at 1 month post-study intervention administration, the 2-sided 95% and 97.5% Cis for group GMT ratios (OA-RSV Group over Adults-HA-RSV Group and OA-RSV Group over Adults-AIR-RSV Group) will be derived from an ANCOVA model on log10-transformed titers for each neutralization *assay*. The model will include the group (OA-RSV Group, Adults-HA-RSV Group and Adults-AIR-RSV Group) and the baseline log10-transformed titer as covariate.

The SRR is defined as the proportion of participants having a fold increase in *neutralization* titers (1 month post-study intervention administration over pre-study intervention administration) ≥4. The 2-sided 95% and 97.5% Cis for group SRR difference (OA-RSV Group minus Adults-HA-RSV Group and OA-RSV Group minus Adults-AIR-RSV Group) will be derived using the method of Miettinen and Nurminen Miettinen, 1985] (Amended: 25 May 2023).

Missing data will not be replaced.

NI for each primary objective will be claimed to be successful if the upper limit of the 2-sided CI for the GMT ratio will be  $\leq$ 1.5 and the upper limit of the 2-sided CI for the SRR difference will be  $\leq$ 0.10, according to the significance level provided by the graphical testing procedure.

The following graphical testing procedure will be applied to control the global type I error at 2.5% (1-sided) [Bretz, 2009].

Refer to Table 14 where H1/H2/H3/H4 labels are assigned.

The initial allocation of  $\alpha$  among the null hypotheses is (0.025, 0, 0, 0), while the propagation rules are specified by the transition matrix:

$$\begin{pmatrix} 0 & 0.5 & 0.5 & 0 \\ 0 & 0 & 1 & 0 \\ 0 & 0 & 0 & 1 \\ 0 & 1 & 0 & 0 \end{pmatrix}$$

The primary analysis set will be the PPS.

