# 9.5. Sample size determination

The target sample size for the study is approximately 1520 participants: 380 participants each in the Adults-HA-RSV Group and Adults-AIR-RSV Group, 190 participants each in the Adults-HA-Placebo Group and Adults-AIR-Placebo Group and 380 participants in the OA-RSV Group.

The sample size in the groups receiving the investigational vaccine is driven by the statistical power to prove the primary NI objectives.

Assuming 342 evaluable participants in each group receiving the investigational vaccine, the power to demonstrate the primary NI objectives following the graphical testing procedure in Section 9.3.1 is presented in Table 16. Power was estimated by 10 000 simulations, using SAS 9.4:

• Individual RSV-A and RSV-B *neutralization* titers at baseline and at 1 month post-study intervention administration were modeled by a multivariate log-normal distribution, means and variance-covariance matrix based on historical data from other RSV OA vaccine clinical trials. The Adults-AIR-RSV Group was assumed to have the same multivariate log-normal distribution of the OA-RSV Group (i.e., same

means and variance-covariance matrix), while the Adults-HA-RSV Group was assumed to have a 1.25-fold higher mean at 1 month post-study intervention administration for both *neutralization titers* (Amended: 25 May 2023).

- Raw p-values were obtained from shifted 1-sided t-tests (for group GMT ratios) and using the method of Miettinen and Nurminen (for group SRR difference). The p-value associated to each NI objective is the maximum between the p-values from the GMT ratio and from the SRR difference (co-primary endpoints).
- P-values associated to each NI objective were compared with the corresponding alpha, as propagated by the graphical testing procedure, to identify which NI objectives were successfully demonstrated at each simulation.

Table 16 Power of primary NI objectives

Objective	Power	
NI in the Adults-HA-RSV Group for the RSV-A strain	>99%	
NI in the Adults-HA-RSV Group for the RSV-B strain	>99%	
NI in the Adults-AIR-RSV Group for the RSV-A strain	93.6%	
NI in the Adults-AIR-RSV Group for the RSV-B strain	82.8%	
All	82.7%	

All=power to demonstrate all primary NI objectives simultaneously; AIR=At increased risk; HA=Healthy adults; NI=Non-inferiority; RSV=Respiratory syncytial virus.

A 10% attrition rate is accounted from enrolled to evaluable participants.

Participants who withdraw from the study will not be replaced.

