4.2.2. Main analytical approach

The primary analysis set will be the PPS. If, in any group, the percentage of vaccinated participants with serological results excluded from the PPS is more than 5%, a second analysis based on the ES will be performed to complement the PPS analysis.

Considering the sampling timepoint at 1-month post-study intervention administration:

- The 2-sided 95% and 97.5% CIs for group GMT ratios (OA-RSV over Adults-HA-RSV group and OA-RSV over Adults-AIR-RSV group) will be derived from an ANCOVA model on \log_{10} -transformed titers for each neutralization assay. The model will include the group and the baseline \log_{10} -transformed titer as covariate. The group GMT ratios will be based on a back transformation of group contrast in the ANCOVA model applied to the logarithmically transformed titers.
- The SRR is defined as the proportion of participants having a fold increase in neutralizing titers (1-month post-study intervention administration over pre-vaccination) ≥ 4 . The 2-sided 95% and 97.5% CIs for group SRR difference (OA-RSV minus Adults-AIR-RSV group and OA-RSV minus Adults-HA-RSV group) will be derived using the method of Miettinen and Nurminen [[Miettinen, 1985](#)].

Success criteria for NI:

NI for each primary objective will be claimed if the upper limit of the 2-sided CI for the GMT ratio will be ≤ 1.5 and the upper limit of the 2-sided CI for the SRR difference will be ≤ 0.10 , according to the significance level provided by the graphical testing procedure detailed in Section 2.1. The RSV-A and RSV-B neutralizing titer's unit used for computation of the GMT ratio and SRR difference will be ED60. Refer to Section 2 for the definition of null and alternative hypotheses associated to each primary NI objective.

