5. SAMPLE SIZE DETERMINATION

The target sample size for the study is approximately 1520 participants: 380 participants each in the Adults-HA-RSV Group and Adults-AIR-RSV Group, 190 participants each in the Adults-HA-Placebo Group and Adults-AIR-Placebo Group and 380 participants in the OA-RSV Group.

The sample size in the groups receiving the investigational vaccine is driven by the statistical power to prove the primary NI objectives.

Assuming 342 evaluable participants in each group receiving the investigational vaccine, the power to demonstrate the primary NI objectives following the graphical testing procedure in Section 2.1 is presented in [Table 4](#). Power was estimated by 10 000 simulations, using SAS 9.4:

- Individual RSV-A and RSV-B neutralizing titers at baseline and at 1-month post-study intervention administration were modeled by a multivariate log-normal distribution, means and variance-covariance matrix based on historical data from other RSV OA vaccine clinical trials. The Adults-AIR-RSV Group was assumed to have the same multivariate log-normal distribution of the OA-RSV Group (i.e., same means and variance-covariance matrix), while the Adults-HA-RSV Group was assumed to have a 1.25-fold higher mean at 1-month post-study intervention administration for both neutralizing antibodies.
- Raw p-values were obtained from shifted 1-sided t-tests (for group GMT ratios) and using the method of Miettinen and Nurminen (for group SRR difference). The p-value associated to each NI objective is the maximum between the p-values from the GMT ratio and from the SRR difference (co-primary endpoints).

- P-values associated to each NI objective were compared with the corresponding alpha, as propagated by the graphical testing procedure, to identify which NI objectives were successfully demonstrated at each simulation.

Table 4 Power of primary NI objectives

Objective	Power
NI in the Adults-HA-RSV Group for the RSV-A strain	>99%
NI in the Adults-HA-RSV Group for the RSV-B strain	>99%
NI in the Adults-AIR-RSV Group for the RSV-A strain	93.6%
NI in the Adults-AIR-RSV Group for the RSV-B strain	82.8%
All	82.7%

All=power to demonstrate all primary NI objectives simultaneously; AIR=At increased risk; HA=Healthy adults; NI=Non-inferiority; RSV=Respiratory syncytial virus.

A 10% attrition rate is accounted from enrolled to evaluable participants. Participants who withdraw from the study will not be replaced.

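### Does the SRR co-primary need a baseline-adjusted companion analysis because the GMT co-primary is adjusted and the OA group is not randomised?

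*SAP*

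**What the plan says.** Each of the four primary objectives has two co-primary endpoints at one month, and both must pass. In the power simulation, "The p-value associated to each NI objective is the maximum between the p-values from the GMT ratio and from the SRR difference" (Protocol 9.5).

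- **GMT ratio** (SAP 4.2.2): ANCOVA on log10 titre. "The model will include the group and the baseline" log10 titre.
- **SRR difference** (SAP 4.2.2): SRR is the proportion with at least a 4-fold rise over the participant's own pre-dose titre. The intervals for the two differences ("OA-RSV minus Adults-AIR-RSV group and OA-RSV minus Adults-HA-RSV group) will be derived using the method of Miettinen and Nurminen") carry no covariate or stratum. Protocol 9.3.1 has the same: "OA-RSV Group minus Adults-AIR-RSV Group) will be derived using the method of Miettinen and Nurminen".
- **Hypotheses** (Protocol 9.1): they are written on the plain group difference. "This must be rejected in favor of the alternative hypothesis that the GMT ratio is ≤1.5 and the SRR difference is ≤10" per cent.
- **Reference group** (Protocol 6.3.2): "All participants in Cohort 2 (OA-RSV Group) will be assigned to receive the RSVPreF3 OA investigational vaccine". It is a separate cohort defined by age.
- **Power** (SAP 5): baseline and one-month titres were modelled jointly. "The Adults-AIR-RSV Group was assumed to have the same multivariate log-normal distribution of the OA-RSV Group", and the sentence goes on to say that means and covariances are equal.

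**The concern.** Measuring each participant against their own baseline does not make SRR independent of baseline. If the post-dose titre rises less than one-for-one with the pre-dose titre, the group with higher baselines reaches a 4-fold rise less often, even when the response given baseline is identical. Randomisation does not protect the OA comparison. Protocol 4.2 also explains the healthy group by saying "since immunogenicity might be impacted by disease and/or age in both those groups".

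The two co-primaries could then disagree. AIR might miss the 0.10 SRR limit with an adjusted GMT ratio near 1. In the other direction, a lower AIR baseline would make the SRR criterion easier to meet. AIR is where the stated power has least room: 93.6% for RSV-A and 82.8% for RSV-B. A supportive SRR difference stratified by baseline quartile, plus a power scenario with unequal baselines, looks like a cheap addition.

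**Working it through.** **1. The stated power.** From the documents: 342 evaluable per group (380 × 0.9), SRR margin 0.10, GMT margin 1.5, one-sided 0.025. The SRRs, SDs and correlations are not given, so the power table cannot be recomputed independently. It can only be back-solved.

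*SRR alone, equal rates p:* power = Φ(0.10/SE − 1.96), with SE = √(2p(1−p)/342).

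| p | SE | 0.10/SE | Power |
|---|---|---|---|
| 0.83 | 0.0287 | 3.48 | 93.6% |
| 0.72 | 0.0343 | 2.91 | 83.0% |

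The RSV-B objective for AIR can be tested only after the RSV-A objective for AIR, so an RSV-B SRR of about 0.765 fits the full testing graph better than 0.72.

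*GMT alone, true ratio 1:* power = Φ(log10 1.5/SE − 1.96), with log10 1.5 = 0.1761 and SE = SD√(2/342).

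| log10 SD | SE | Power |
|---|---|---|
| 0.40 | 0.0306 | >99.9% |
| 0.66 | 0.0505 | 93.7% |
| 0.79 | 0.0604 | 83.0% |

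Either endpoint can therefore account for the stated AIR powers. Simulation through the full graph with log10 SD 0.4 and SRRs of 84% and 76.5% gave 93.9-94.2% for RSV-A and 82.6-83.2% for RSV-B. That is agreement by construction, because the SRRs were chosen to match. These runs used ANCOVA for the GMT test, whereas the sponsor's used shifted t-tests. A second simulation with t-tests, SRRs of 83% and 76.5%, and somewhat different variance inputs gave 92.9% and 82.1%.

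**2. Size of the SRR shift.** Assume equal pre and post SD of 0.4, correlation ρ, and the same response given baseline in AIR and OA. Let AIR baseline be f times higher and z = Φ⁻¹(SRR).

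- SD of the log fold rise: 0.4√(2(1−ρ))
- Change in mean log fold rise for AIR: −(1−ρ)·log10 f
- AIR SRR: Φ(z − (1−ρ)·log10 f / SD of log fold rise)

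For f = 1.2, ρ = 0.5 and SRR 76.5%, z = 0.7225, log10 1.2 = 0.0792 and the SD is 0.4. The shift in z is 0.5 × 0.0792/0.4 = 0.0990, and Φ(0.6235) = 73.35%. The difference is 3.15 points.

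| AIR baseline | SRR 84%, ρ 0.3 / 0.5 / 0.7 | SRR 76.5%, ρ 0.3 / 0.5 / 0.7 |
|---|---|---|
| 1.1-fold higher | 1.5 / 1.3 / 1.0 | 1.9 / 1.6 / 1.2 |
| 1.2-fold higher | 3.0 / 2.5 / 1.9 | 3.7 / 3.2 / 2.4 |
| 1.2-fold lower (favours NI) | 2.7 / 2.3 / 1.8 | 3.4 / 2.9 / 2.3 |

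In simulation, quartile stratification left 0.3-0.4 points of the 1.2-fold shift. The shift is zero if post-dose titre rises one-for-one with pre-dose titre.

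**3. What the planned outputs already show.** SAP 4.3.2.2.2 gives, per group and time point, unadjusted GMTs, the percentage with a 4-fold rise, mean geometric increases (MGIs) and reverse cumulative curves. With ANCOVA slope b and the same participants,

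log MGI ratio (OA/AIR) = log adjusted GMT ratio − (1 − b) × baseline log difference (OA − AIR).

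Subtracting the adjusted log GMT ratio from the log MGI ratio therefore isolates the baseline contribution on the scale that SRR dichotomises. In the example of step 2 the adjusted ratio is 1 and the MGI ratio is 10^(0.5 × 0.0792) = 1.095, so baseline accounts for all of it. What this does not give is a conversion into SRR percentage points.

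**4. What a stratified table would add.** It would change no hypothesis, margin, alpha, sample size or decision. In the simulations with equal baselines, 25-46% of AIR failures on the primary SRR criterion still had a stratified upper limit within 0.10. With AIR 1.2-fold higher it was 58-80%. A passing stratified interval beside a failed primary one would thus be common with no imbalance at all, and a reader would still have to go to the baseline GMTs.

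**The case for a change.** The best case for acting is that the mechanism is sound and its size is not trivial: 2 to 4 points of a 10-point margin at a 1.2-fold difference. On the assumed inputs, a 1.1-fold higher AIR baseline would lower the simulated RSV-B power from about 83% to 61-69%. The table needs only titres that the per-protocol set already requires, and no visible text expresses the baseline contribution in SRR points.

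The mechanism stands, and so does the narrow gap in SRR points. The power figures do not support a change. They describe the plan under a hypothetical imbalance, and the table would leave them as they are. They also require SRR to be the limiting endpoint, which step 1 shows is only one of two readings. The request to state the equal-baseline assumption falls away, because Protocol 9.5 and SAP 5 state it. Protocol 4.2 says only that disease or age might affect immunogenicity. It does not mention pre-vaccination titre, and a different response to vaccine is what the trial sets out to test. Finally, the SAP version history shows that Section 4.4.1 gained an exploratory analysis whose content is redacted, so absence cannot be established.

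**Conclusion.** No change to the plan is called for. The unstratified Miettinen-Nurminen interval estimates the quantity that the four hypotheses name. Adjusting one co-primary and not the other is a coherent choice: each objective must pass both, so a favourable SRR shift from a low baseline cannot carry an objective whose adjusted GMT ratio fails.

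The possible distortion of the SRR difference is 1.0-1.9 points at a 1.1-fold baseline difference and 1.9-3.7 points at 1.2-fold. This assumes log10 SD 0.4, correlation 0.3-0.7, SRR of 84% and 76.5%, and equal response given baseline. None of these inputs is in the documents, and nothing there indicates an imbalance or its direction. If one occurs, the planned baseline GMTs, MGIs and adjusted GMT ratio will reveal it. A stratified SRR difference can still be run from the same data as an exploratory aid, without any non-inferiority claim. Its absence from the visible text is not a defect.

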4.3. Secondary Endpoint(s) Analyses

4.3.1. Definition of endpoints

Refer to Section 1.1 for the definition of secondary safety and immunogenicity (humoral and CMI response) endpoints.

4.3.2. Main analytical approach

4.3.2.1. Safety analysis

The safety analysis will be performed per study group, on the ES, as follows:

- The number and percentage of participants with at least one administration site event (solicited and unsolicited), with at least one systemic event (solicited and unsolicited) and with any AE (solicited and unsolicited) during the 4-day or 30-day follow-up period after vaccination will be tabulated with exact 95% CI. The same computations will be done for Grade 3 AEs, for Grade 3 non-serious AEs and for AEs resulting in a medically attended visit.

Those analyses will present all solicited and unsolicited AEs, including SAEs (unless otherwise specified).

- The number and percentage of participants with at least one administration site event (solicited only), with at least one systemic event (solicited only) and with any solicited event during the 4-day follow-up period after vaccination will be tabulated with exact 95% CI. The same computations will be done for Grade 3 AEs and for AEs resulting in a medically attended visit.
- Compliance in completing solicited events information will be tabulated.
- The number and percentage of participants reporting each individual solicited administration site or systemic event (any grade, Grade 3 and resulting in medically attended visit) during the 4-day follow-up period after vaccination will be tabulated with exact 95% CI.
- For fever, the number and percentage of participants reporting fever by half degree ($^{\circ}\text{C}$) cumulative increments during the 4-day follow-up period after vaccination will be tabulated.

- The percentage of participants with each solicited administration site event and solicited systemic event (any grade and Grade 3) during the 4-day follow-up period after vaccination will be represented graphically.
- The duration in days of each individual solicited events will be tabulated using descriptive statistics (mean, min, Q1, median, Q3, maximum).
- The number of days with Grade 3 solicited events will be tabulated for each individual solicited event using descriptive statistics (mean, min, Q1, median, Q3, maximum).
- The number and percentage of participants with any unsolicited AEs during the 30-day follow-up period with its exact 95% CI will be tabulated by group and by MedDRA Primary System Organ Class (SOC), High Level Term (HLT) and Preferred Term (PT). Similar tabulation will be done for Grade 3 unsolicited AEs, for any causally related unsolicited AEs, for Grade 3 causally related unsolicited AEs and for unsolicited AEs resulting in a medically attended visit. The analyses of unsolicited AEs will include SAEs, AESIs (including pIMDs and AF), unless otherwise specified.
- The number and percentage of participants with any non-serious unsolicited AEs during the 30-day follow-up period with its exact 95% CI will be tabulated by group and by MedDRA Primary System Organ Class (SOC), High Level Term (HLT) and Preferred Term (PT). Similar tabulation will be done for Grade 3 non-serious unsolicited AEs, for any causally related non-serious unsolicited AEs, for Grade 3 causally related non-serious unsolicited AEs and for non-serious unsolicited AEs resulting in a medically attended visit.
- The number and percentage of participants with any unsolicited AEs reported within 30 minutes following vaccination with its exact 95% CI will be tabulated by group and by MedDRA Primary System Organ Class (SOC), High Level Term (HLT) and Preferred Term (PT). Similar tabulation will be done for Grade 3 unsolicited AEs reported within 30 minutes following vaccination.
- The verbatim reports of unsolicited AEs, including SAE and AESI, will be reviewed by a qualified person and the signs and symptoms will be coded according to the MedDRA Dictionary for Adverse Reaction Terminology. Every verbatim term will be matched with the appropriate Preferred Term.
- The number and percentage of participants with at least one report of SAE classified by the MedDRA Primary SOC, HLT and PT from vaccination up to Month 6 will be tabulated with exact 95% CI.
- The number and percentage of participants with at least one report of SAE classified by the MedDRA Primary SOC, HLT and PT, related to study intervention administration, from vaccination up to Month 6 and study end (Month 12) will be tabulated with exact 95% CI.
- The number and percentage of participants with any fatal SAE, from vaccination up to Month 6 and study end (Month 12) will be tabulated with exact 95% CI.

- The number and percentage of participants with at least one report of pIMD classified by the MedDRA Primary SOC, HLT and PT from vaccination up to Month 6 will be tabulated with exact 95% CI.
- The number and percentage of participants with at least one report of pIMD classified by the MedDRA Primary SOC, HLT and PT, related to study intervention administration, from vaccination up to Month 6 and study end (Month 12) will be tabulated with exact 95% CI.
- The number and percentage of participants with specific Demyelinating disorder with onset within 30 days of vaccination will be tabulated with exact 95% CI.
- The number and percentage of participants with specific Serious Demyelinating disorder from vaccination up to Month 6 and study end (Month 12) will be tabulated with exact 95% CI.
- All SAEs/AESIs (including pIMDs and AF) up to study end (Month 12) will also be described in detail in a tabular listing.
- AEs/SAEs leading to study discontinuation from vaccination up to study end will be tabulated.
- For web posting purposes, the number of occurrences and the number and percentage of participants with non-serious AEs (solicited and unsolicited combined) during the 30-day follow-up period (i.e., the day of vaccination and 29 subsequent days) will be produced by SOC and PT.
- In case of pregnancies, these will be described in detail.
- In case participants belonging to the OA stratum receive placebo (i.e., participants eliminated from the ES following code 1100, refer to Section 3.1.2), SAEs and AESIs (including pIMDs and AF) reported (if any) will be described.
- AF AESIs will be tabulated within the summary of AEs or SAEs according to their classification.

For analysis of SAEs/AESIs (including pIMD and AF) within 6 months after vaccination, the reporting period will start at vaccination and will end at Day 183 after each dose, computed as 6×30.5 days = 183 days.

Refer to Section 6.1.5 and Section 6.1.6 for the analysis of concomitant medications and concomitant vaccination.

